The INSPIRE-ASP Trial (INtelligent Stewardship Prompts to Improve Real-time Empiric Antibiotic Selection for Patients) for Abdominal (ABD) Infections Protocol

NCT:05423743

6/24/2020

Brief Overview

The **INSPIRE-ASP Trial (INtelligent Stewardship Prompts to Improve Real-time Empiric Antibiotic Selection for Patients) for Abdominal (ABD) Infections** is a cluster-randomized trial of 92 hospital randomized units (102 individual hospitals) to improve physicians' choice of antibiotics for patients hospitalized with ABD infections by reducing the unnecessary use of extended-spectrum antibiotics. This trial provides prescribers in half the hospitals with prescribing advice based on the probability that a patient is infected with antibiotic resistant bacteria. Provision of unnecessary extended-spectrum antibiotics carry risks, and the goal of this trial is to limit their use to situations in which the patient is likely to require them, while maintaining excellent patient outcomes.

We hypothesize that providing clinicians with individual patient risk estimates for antibiotic-resistant infections will reduce the overuse of empiric extended-spectrum antibiotics among patients hospitalized for ABD infections. To do this, we will use patient information in the electronic health record plus local hospital laboratory data on antibiotic resistance in ABD cultures to develop an automated smart tool that provides the likelihood that a patient needs extended-spectrum antibiotics. 102 hospitals were randomized into 92 hospital units, into either routine care (46 hospital units) or to the intervention arm (46 hospital units) receiving the INSPIRE Stewardship Bundle which includes CPOE smart prompts, clinician feedback reports, and activities to support CPOE adoption (e.g., education and modifications of CPOE workflows as needed). In half of these hospitals, physicians will be prompted to use standard-spectrum antibiotics when the risk of antibiotic-resistant infection is low. This 12-month intervention will evaluate approximately 99,000 patients with ABD infections.

Protocol Summary

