This protocol provides detailed instructions for the conduct of the INSPIRE-ASP Trial (INtelligent Stewardship Prompts to Improve Real-time Empiric Antibiotic Selection for Patients) for Abdominal (ABD) Infections. This trial is a 92 hospital unit (102 individual hospitals), 99,000 patient cluster-randomized trial to improve physicians' choice of antibiotics for hospitalized patients by reducing the unnecessary use of extended-spectrum antibiotics while maintaining excellent patient outcomes. This trial will be conducted in the HCA Healthcare system, which provides 5% of acute care services in the United States.

Hospitals will be recruited through usual HCA Healthcare communication channels and randomized into a two-arm trial involving routine care or routine care plus a stewardship bundle that includes real-time personalized risk calculator for whether a patient with ABD infection is infected with an antibiotic-resistant pathogen warranting extended-spectrum antibiotic therapy. This protocol details eligibility criteria for participation, factors accounted for in 1:1 hospital randomization, notification of randomization assignment, and provision of the two arms with arm-specific toolkit information and coaching calls. It also details the process by which centralized IRB approval and reliance agreements will be obtained.

This trial evaluates a quality improvement antibiotic stewardship strategy, the INSPIRE Stewardship Bundle, that includes (1) computerized physician order entry (CPOE) decision support alert that provides physicians with patient-specific risk estimates for having a (ABD) infection due to a multidrug-resistant organism (MDRO) and recommends standard spectrum antibiotics for low risk patients in the first 3 days of hospitalization; (2) clinician feedback reports, and (3) activities to support CPOE adoption (including education and alignment of CPOE workflows). As such, all implementation will be performed through the local infrastructure provided by hospital antibiotic stewardship program leaders who serve as study champions. Participating hospitals in both arms will approve the arm-specific study protocol through usual hospital committees. The routine care arm will participate in regular coaching calls to ensure best practice for national standards of stewardship are taught and encouraged. This arm will also launch trial-specific modifications to the existing antibiotic indication screens.

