The primary trial outcome is defined as the summed number of different ES antibiotics received during each empiric day. An empiric day is a day within the first three days of an admission. We define this outcome as the Total Empiric Extended-Spectrum Days of Therapy (ES-DOT). For clarity, the calculation is as follows: we define a DOT for a particular ES antibiotic as a day in which any number of doses of that antibiotic is given. Different ES antibiotics are summed within each empiric day for each patient admission to determine DOT in that at-risk day. Antibiotics given during an associated emergency department visit on the date of hospital admission are counted toward the ES-DOT of the first hospital day.

The main trial results will be based upon as-randomized, unadjusted analyses of admission-level ES-DOT. In contrast to the national DOT measure defined by CDC for hospitals, we define ES-DOT at the individual admission level so that we can perform analyses on individuals.

The trial will be assessed among the cohort of adult admissions who: 1) have administrative claims codes indicating an abdominal infection is present on admission; 2) received any antibiotic within 3 days of admission; and 3) were admitted to a non-ICU location. For admissions initially on a non-ICU floor and transferred to the ICU, analysis will include only admission days on the non-ICU floor within 3 days of admission.

The trial periods are defined as follows: (1) Baseline: January 1, 2019 – December 31, 2019 (12 months); (2) Phase-in: August 2, 2022 – December 31, 2022 (5 months, does not contribute to analysis); (3) Intervention: January 1, 2023 – December 30, 2023 (12 months). The main evaluation of all outcomes will be difference-in-difference between the Intervention and Baseline periods and between study arm. Trial analysis will use a baseline period prior to the arrival of the COVID-19 pandemic since hospital operations and case mix were severely impacted by this pandemic between Winter 2020-Spring, 2022.²⁵⁻²⁹ Although at the time of this

writing (June, 2022), COVID-19 surges continue to occur nationally, clinical operations and patient case mix at most hospitals have largely returned to near pre-pandemic activity in the setting of widespread vaccination and milder virus strains. Phase-In is scheduled for August, 2022 as participating hospitals are in a state of recovery sufficient to launch the trial intervention with pharmacy/physician engagement.

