The unit of analysis will be individual admissions. Individuals can contribute more than one admission. The analytic model will be a generalized linear mixed effects model for differences in differences, with random effects accounting for correlation within cluster, period-varying random effects to allow for differences within hospitals between baseline and follow-up, and admission-level random effects to account for correlation within person and hospital, if sufficient data exist. We plan to use a Poisson model for analysis of outcomes as follows:

$$\log(y_{ijph}) = \beta_0 + \beta_1 A_{ijph} + \beta_2 T_{ijph} + \beta_3 A_{ijph}T_{ijph} + b_{0h} + b_{1h}T_{ijph} + g_j + \log(ed_j)$$

where y_{ijph} is the ES-DOT for patient i for admission j in period p at hospital h , and $A_{ijph} = 1$ if hospital h is in the intervention arm and 0 if not, and $T_{ijph} = 1$ if p is the intervention period and 0 if baseline period. The random effects b_{0h} and b_{1h} allow for different baseline mean admission-level ES-DOT for each hospital and each hospital in the intervention period, respectively. Equivalently, they allow for correlation within hospital at different levels at baseline and at follow-up. The random effect g_j allows each patient to have a different mean ES-DOT. Finally, ed_j is the number of empiric days in the admission.

The assessment of trial success will be determined by the significance of the arm by period interaction term β_3 , which assesses whether the log relative rate of the outcome due to being in the intervention arm in the intervention period is different from 0. The exponentiated parameter estimate for β_3 is the estimated relative rate of ES-DOT per at-risk day due to the intervention, relative to the baseline period. For example, if β_3 had a negative value and a p-value <0.05 , we would conclude that the patient-specific CPOE smart prompts generated a benefit over routine care. Exponentiating the parameter value would provide an estimate of the relative reduction due to the intervention in the expected ES-DOT per at-risk day.

The primary trial analysis will use an as-randomized unadjusted model with two-tailed significance set at alpha = 0.05. Secondary outcomes will be assessed using an as-randomized unadjusted model and will include adjustment for multiple comparisons with two-tailed significance set at alpha = 0.025 for the two secondary outcomes.

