Subsequent analyses of the primary and secondary outcomes will include both as-treated and adjusted models. Adjusted models will account for individual characteristics such as age, gender, comorbidities, and prior history of MDROs as well as hospital characteristics such as hospital antibiotic resistance. We will also account for seasonality. All adjusters will be determined a priori. These analyses will be reported as point estimates with confidence intervals and without p-values. The reason for including these analyses is to provide additional information related to the trial outcomes for readers to assess the effects of potential confounders. The reason to not include them in a formal multiple comparisons adjustment is because these analyses are non-independent evaluations relative to the as-randomized unadjusted analyses.

We will separately evaluate intervention period effects by arm alone.

Safety Outcomes

Safety outcomes noted in the above table will be assessed in the most conservative manner to identify potential safety issues. Safety outcomes are required because a reduction in ES-DOT might be achieved only by incorrectly withholding ES antibiotics when they were really needed. Each safety outcome will be evaluated for non-inferiority using an as-randomized unadjusted analysis with a one-tailed significance set at alpha = 0.05. Length-of-stay and days to ICU transfer are evaluated within 14 days of admission since empiric antibiotic selection within the first 3 hospital days is not expected to be a main driver of either outcome beyond this time period; evaluation of baseline data also shows that 93% of abdominal patients have length-of-stay equal to or less than 14 days. Analyses planned for these assessments are proportional hazards models with random effects for each hospital and admission. These models are sometimes called frailty or shared frailty models. Because these are safety outcomes, we do not intend to make adjustments for multiple comparisons in testing them, further increasing conservatism.

All analyses will be performed using current versions of SAS (Version 9.4, as of writing, SAS Institute, Cary NC) and/or R (Version 4.0, as of writing).

C.2.11 Power Size/Sample Size Calculations

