Power assessment proceeded as follows, using a Monte Carlo approach.²⁵ We used available data to define a baseline period of 1/1/2019-12/31/2019. In a bootstrap procedure, individuals were selected with replacement from within each hospital, once to represent baseline data and separately to represent “intervention period” data. Hospitals were then “randomized” to intervention or control according to multiple parameters, including number of admissions with abdominal infection and ES-DOT. We then modified the outcomes for the bootstrapped individuals in the “intervention” period in the “intervention” arm to reflect the effect of the intervention.²⁹

We assessed power to identify an overall 12.5% relative reduction in ES-DOT. This effect was implemented by reducing the relative empiric days of therapy for each admission which was exposed to the CPOE prompt. The amount of reduction was a uniform random variate between 0.75 and 1. For example, if the bootstrapped patient initially received 8 ES-DOT and was assigned to have a 12.5% reduction, then that admission intervention ES-DOT would be reduced to 7 days ($8*0.875=7$). The reduction of ES-DOT was selected with a lower bound determined by the investigators as the minimal effect achieved that would be clinically meaningful. Using this method, we have $\geq 99.9\%$ (99.6-99.9%) power to detect this effect.

Since adoption of the intervention will be heavily influenced by the ability to demonstrate safety, our study size was based on the power to detect non-inferiority for safety outcomes. We used methods similar to the above to calculate the power to identify at least a one day increase in length-of-stay for 12.5% of patients who had hospitalizations less than 14 days and found the power was 91.5% (CI 89.6-93.2%), where non-inferiority is defined as a hazard ratio no smaller than 0.98. For days to ICU transfer, we estimated the power to detect a 2% increase in transfers to the ICU on hospital day 3 through 14 to be $>99.9\%$ (CI 99.6-99.9%), where non-inferiority is defined as having a hazard ratio no greater than 1.1 (fewer days to ICU results in a hazard ratio above 1).

For completeness, we note that there are other pre-specified outcomes intended for exploratory analysis in secondary papers for the INSPIRE ABD trial in Table 4 below.

Table 4: Secondary Manuscripts - Other Pre-Specified Outcomes

Secondary Manuscripts (other pre-specified secondary exploratory analyses for later manuscripts)	

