The primary trial analysis will use an as-randomized unadjusted model with two-tailed significance set at alpha = 0.05. Secondary outcomes will be assessed using an as-randomized unadjusted model and will include adjustment for multiple comparisons with two-tailed significance set at alpha = 0.025 for the two secondary outcomes.

Subsequent analyses of the primary and secondary outcomes will include both as-treated and adjusted models. Adjusted models will account for individual characteristics such as age, gender, comorbidities, and prior history of MDROs as well as hospital characteristics such as hospital antibiotic resistance. We will also account for seasonality. All adjusters will be determined a priori. These analyses will be reported as point estimates with confidence intervals and without p-values. The reason for including these analyses is to provide additional

information related to the trial outcomes for readers to assess the effects of potential confounders. The reason to not include them in a formal multiple comparisons adjustment is because these analyses are non-independent evaluations relative to the as-randomized unadjusted analyses.

Safety Outcomes

Safety outcomes are required because a reduction in ES-DOT might be achieved only by incorrectly withholding ES antibiotics when they were necessary. Each safety outcome will be evaluated for non-inferiority using an as-randomized unadjusted analysis with a one-tailed significance set at alpha = 0.05. For length of stay, the non-inferiority margin is a hazard ratio of 0.98. For days to ICU transfer, the non-inferiority margin is a hazard ratio of 1.1 (fewer days to ICU results in a hazard ratio above 1). Analyses planned for these assessments are proportional hazards models with random effects for each time period, hospital, and admission. These models are sometimes called frailty or shared frailty models. Because these are safety outcomes, we do not intend to make adjustments for multiple comparisons in testing them, further increasing conservatism. As above, it may not be possible to include multiple admissions.

All analyses will be performed using current versions of SAS/STAT and/or R packages lme4 and coxme, unless better packages become available in the meantime.

Further Planned Analyses

We note that there are other pre-specified outcomes intended for exploratory analysis in secondary papers for the INSPIRE ABD trial in Table 5 below.

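### If hospital allocation was balanced on volume and ES-DOT, the unadjusted models without factor-by-period terms give somewhat conservative tests; the cost is precision, at most modest and confined to length of stay

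*Protocol*

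**What the plan says.** The Protocol Summary says that the protocol sets out the "factors accounted for in 1:1 hospital randomization". Section E.1 (Randomization) covers timing and notification but names no factor and no method, and the SAP does not mention either. The only named factors are in C.2.11, where the mock hospitals of the power simulation are allocated "according to multiple parameters, including number of admissions with abdominal infection and ES-DOT". The Brief Overview describes 92 units allocated "into either routine care (46 hospital units) or to the intervention arm (46 hospital units").

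On the analysis, the SAP (Primary Statistical Analysis) states: "The primary trial analysis will use an as-randomized unadjusted model with two-tailed significance set at alpha = 0.05". The secondary outcomes are handled in the same way. For safety, protocol H.3 states: "Each safety outcome will be evaluated for non-inferiority using an as-randomized unadjusted analysis with a one-tailed significance set at alpha = 0.05". The primary model contains arm, period, arm-by-period, hospital and patient random effects and an offset for empiric days. Neither document puts a balancing factor, or a factor-by-period term, into the primary, secondary or safety models.

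The plan does use baseline data: "The main evaluation of all outcomes will be difference-in-difference between the Intervention and Baseline periods and between study arm". The hospital random effects in the primary model "allow for different baseline mean admission-level ES-DOT for each hospital and each hospital in the intervention period, respectively". Supportive adjusted models are planned for the primary and secondary outcomes, without p-values. The one hospital characteristic they name is antibiotic resistance. No adjusted model is planned for the safety outcomes.

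**The concern.** When allocation is forced to be balanced on a factor that predicts the quantity being compared, the treatment contrast varies less from one possible allocation to the next than a model without that factor assumes. The model-based SE is then too large and the test rejects too seldom.

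Here the quantity compared is each hospital's change from 2019 to 2023. Differencing removes whatever is constant within a hospital. It leaves any part of the change that depends on the balancing factors. Regression to the mean is the plainest route: a hospital with unusually high ES-DOT in 2019 will tend to fall back by 2023 in either arm, unless the two years are almost perfectly correlated. Larger hospitals might also change differently from smaller ones.

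What is at stake is precision. C.2.11 says that the trial was sized on the safety non-inferiority tests, so those are where lost precision could count.

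**Working it through.** **The plan's own figures.** C.2.11 gives bootstrap power of at least 99.9% for the primary outcome (interval 99.6% to 99.9%), 91.5% for length of stay (interval 89.6% to 93.2%, margin 0.98) and more than 99.9% for ICU transfer (margin 1.1). The length-of-stay interval matches 1,000 replicates: the exact binomial interval for 915/1,000 is 89.6% to 93.2%. For 1,000/1,000 the exact lower limit is 99.6%. The power values themselves cannot be rebuilt, because the hospital-level 2019 data behind them are not given.

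**Size of the SE excess.** Inputs: 92 units, 46 per arm (Brief Overview); balance on the baseline value of the outcome (assumption); correlation rho between a hospital's baseline and intervention values (assumption, not in the documents); equal variance in the two periods, scaled to 1; between-unit variance dominating the variance of the effect estimate (assumption).

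- Variance of change, baseline left out: 2(1 − rho).
- Variance of change given baseline: 1 − rho² = (1 − rho)(1 + rho).
- Correct SE / unadjusted SE: k = √[(1 + rho)/2].
- Actual error of the unadjusted test: 2[1 − Φ(1.960/k)] two-sided, 1 − Φ(1.645/k) one-sided.

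| rho | k | SE excess, 1/k − 1 | Two-sided 5% becomes | One-sided 5% becomes |
|---|---|---|---|---|
| 0.5 | 0.866 | 15.5% | 2.4% | 2.9% |
| 0.7 | 0.922 | 8.5% | 3.4% | 3.7% |
| 0.8 | 0.949 | 5.4% | 3.9% | 4.1% |
| 0.9 | 0.975 | 2.6% | 4.4% | 4.6% |
| 0.95 | 0.987 | 1.3% | 4.7% | 4.8% |

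A simulation of 92 units, pair-matched on baseline (4,000 runs per rho), agrees. The ratio of true to model SE was 0.86, 0.93, 0.96, 0.97 and 0.99 for the five rows, an excess of about 1% to 8% for rho 0.7 to 0.95. The unadjusted two-sided error ran from 2.1% at rho 0.5 to 4.5% at 0.95. With baseline and volume as covariates for change, which is what factor-by-period terms do, the error was 4.4% to 5.8% and the SE matched the true spread.

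**If sampling variation within hospitals also counts.** At rho 0.7 the factor explains 1 − (1 + rho)/2 = 15% of the between-unit variance of change. If that variance is only half of the total (assumption), the excess is 1/√(1 − 0.5 × 0.15) − 1 = 4.0% instead of 8.5%. At rho 0.95 the same step gives 1/√(1 − 0.5 × 0.025) − 1 = 0.6% instead of 1.3%.

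**Main effects alone.** A hospital-level factor is the same in both periods, so as a main effect it cancels from each hospital's change. In a linear mixed model with a hospital random effect (one simulated data set), the SE of beta3 was 0.1204 both without and with the main effects. That data set shows only that main effects do nothing. The recovery of precision comes from the repeated simulation above.

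**Effect on power.** Take the stated power as that of the unadjusted test and multiply its SE by r.

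- Length of stay, one-sided 0.05: Φ[(1.645 + 1.372)/r − 1.645]. For r = 0.98 this is Φ(1.434) = 92.4%; for r = 0.95, Φ(1.531) = 93.7%.
- Primary, two-sided 0.05, starting from 99.9%: Φ[(1.960 + 3.090)/r − 1.960]. For r = 0.98 this is 99.93%; for r = 0.95, 99.96%.

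**The case against.** The strongest reply is that the plan already uses each hospital's own baseline. Baseline ES-DOT, one of the two named factors, enters the primary model as outcome data from 2019. A reader might infer that the models ignore the randomisation factors altogether; that goes too far. What remains out of the models is only the part of the change that depends on the factors. The documents do not show how large that part is.

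Second, the only factors named belong to the simulated allocation. A reader might take volume and ES-DOT as the factors actually used, but E.1 does not say so, and stratified, paired and constrained allocation cannot be told apart from the text. This stands, and it is why the conclusion is conditional.

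Third, a wider SE makes non-inferiority harder to claim, and H.3 says that safety is to be judged as conservatively as possible. That is a fair reason to accept the unadjusted test. Still, the added strictness is unquantified and comes on top of the declared one-sided 0.05.

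Fourth, the stated power might already carry the penalty, since the simulation used the balancing. C.2.11 does not say which model was fitted. However, both simulated periods are resampled from the same 2019 data within hospital. Real 2019-to-2023 change related to volume or ES-DOT is therefore absent, and the 91.5% cannot contain that loss.

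Fifth, volume and ES-DOT need not predict change in length of stay. This stands and lowers the likely gain.

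Finally, the SAP is dated 3/29/2024, after the intervention year ended, so replacing the primary model could look like post-hoc choice. This affects timing and reporting but does not remove the gain in precision.

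**Conclusion.** The point holds as one of precision and reporting. If allocation was balanced on volume, ES-DOT or similar factors, the unadjusted models overstate the SE of the arm-by-period effect and the tests are conservative. The calculation gives no support for reading this as bias, inflated type I error or an invalid primary analysis; the error runs the other way.

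The size cannot be taken from the documents. The excess of about 1% to 8% rests on the assumed correlations of 0.7 to 0.95, balance on the baseline outcome and dominant between-unit variance. It would be larger at lower correlation, which four years and a pandemic between the periods do not rule out, and smaller where within-hospital variation matters.

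With stated power of at least 99.9%, the primary and ICU-transfer tests are not materially affected. For length of stay, 91.5% would become roughly 92% to 94% if the SE fell by 2% to 5%, taking the stated figure at face value, and would change less if the factors only weakly predict change in that outcome.

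**What to change.** 1. State in E.1 and in the SAP the factors and the method used to randomise the 92 units.
2. Prespecify factor-by-period terms in the primary, secondary and Cox safety models: unit-level baseline volume and ES-DOT, or the strata or pairs if those were used. Main effects alone, the usual remedy in a single-period trial, would leave the SE of beta3 unchanged.
3. Make the change before any unblinded comparison, and report the unadjusted model alongside.

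The cost is an amendment to the prespecified model and a few degrees of freedom among 92 units. The baseline values needed are already held.

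### The 91.5% length-of-stay power on which study size rests is not the power of the planned difference-in-differences non-inferiority test, which is about 70% at a true hazard ratio of 1 with 99,000 admissions per period

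*Protocol*

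**What the plan says.** Protocol C.2.11 (Power Size/Sample Size Calculations) states that "our study size was based on the power to detect non-inferiority for safety outcomes". The LOS calculation is introduced with "We used methods similar to the above to calculate the power to identify", and its target is "power to identify at least a one day increase in length-of-stay for 12.5% of patients who had hospitalizations less than 14 days". The authors "found the power was 91.5% (CI 89.6-93.2%), where non-inferiority is defined as a hazard ratio no smaller than 0.98".

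The method referred to is the bootstrap for the primary outcome, in which "individuals were selected with replacement from within each hospital, once to represent baseline data and separately to represent" the intervention period. Hospitals were then allocated to arms, and the imposed effect is described by "We then modified the outcomes for the bootstrapped individuals in the" intervention period of the intervention arm.

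For ICU transfer, "we estimated the power to detect a 2% increase in transfers to the ICU on hospital day 3 through 14 to be" above 99.9%, against a margin of HR 1.1.

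On the analysis, Protocol H.3 says: "The main evaluation of all outcomes will be difference-in-difference between the Intervention and Baseline periods and between study arm". The SAP (Primary Statistical Analysis) says the same. Both documents test the safety outcomes for non-inferiority at one-sided alpha 0.05, with a LOS margin of HR 0.98. The SAP's frailty model includes a random effect for time period.

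**The concern.** Non-inferiority power is the probability of ruling out the margin when the true effect is acceptable, usually HR 1. The LOS paragraph instead imposes a lengthening of stay and then quotes a power beside the non-inferiority margin. It does not give the HR that the shift implies, the contrast fitted or the decision rule. A reader will take 91.5% as the chance that the trial demonstrates LOS safety.

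The protocol says adoption depends on demonstrating safety. If the true power is well below 91.5%, an inconclusive LOS result is more likely than advertised, and it could be misread as a signal of harm from a well-powered test. The risk is an inconclusive result judged against an overstated power, not a false claim of safety.

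**Working it through.** **Inputs from the documents.** LOS margin HR 0.98, so |ln 0.98| = 0.0202. One-sided alpha 0.05, z = 1.645. About 99,000 patients in the 12-month intervention period (Protocol Brief Overview), or 60,000 by the closing paragraph of the Protocol Summary. Allocation 46:46 units. 93% of stays end by day 14 (Protocol H.3, Safety Outcomes).

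**Assumptions.** Patients are counted as admissions. The baseline count is not stated and is taken as equal unless varied. Hospital-by-period variance is zero.

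**1. The stated interval.** 89.6–93.2% is the exact binomial 95% interval for 915 successes in 1,000 simulations, so 91.5% is a simulated rejection rate. The question is what was rejected.

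**2. HR implied by the imposed shift.** The large-sample Cox estimate was computed for 24 daily-discretised stay distributions: lognormal, Weibull, gamma and log-logistic, with medians 2.5, 3, 4, 5, 6 and 7 days. All had 93% at or below 14 days, and 12.5% of stays under 14 days were moved by one day.

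- Efron ties: HR 0.9693 to 0.9786.
- Breslow ties: HR 0.9727 to 0.9796.

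Every value is below 0.98.

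**3. Precision of the difference-in-differences contrast.** Events per cell = 49,500 × 0.93 = 46,035. SE(ln HR) = √(4/46,035) = 0.00932.

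**4. Power under the imposed shift.**

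| | Non-inferiority concluded | Harm detected (one-sided 0.05) |
|---|---|---|
| Formula | Φ((ln HR + 0.0202)/SE − 1.645) | Φ(−ln HR/SE − 1.645) |
| Efron | 0.2–3.6% | 75–96% |
| Breslow | 0.7–4.6% | 71–91% |

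The stated 91.5% lies far outside the first column and inside the range of the second.

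**5. Planned test at true HR 1.** Power = Φ(0.0202/0.00932 − 1.645) = 69.9%.

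- 60,000 per period: 27,900 events per cell, SE 0.01197, power 51.7%.
- 99,000 in the intervention period with a different baseline, SE = √(2/46,035 + 2/(0.93 × baseline/2)): 60,000 gives 59.4%, 80,000 gives 65.7%, 120,000 gives 73.4%.
- Other true HRs at 99,000 per period: 0.995 gives 49%, 1.005 gives 85%, 1.01 gives 94%.
- Illustrative hospital-by-period SD on the log hazard, adding 4 × SD²/92 to the variance: 0.02 gives 63%, 0.03 gives 56%, 0.05 gives 42%. The documents give no value.

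Reaching 91.5% needs 4 × ((1.645 + 1.372)/0.0202)² ≈ 89,209 events per cell, or 2 × 89,209/0.93 ≈ 191,800 admissions per period.

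**6. Intervention period alone at HR 1.** SE = √(2/46,035) = 0.00659, power 92.2%. This is numerically close to 91.5%, but it is not the planned main contrast. It also assumes no between-hospital variance: an SD of 0.02 on the log hazard reduces it to 83%, and 0.05 to 50%.

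**7. Simulation check.** 1,000 four-cell trials per setting were fitted by a Cox model with arm, period and interaction (Efron ties; lognormal medians 3 and 4, Weibull median 5). At HR 1, non-inferiority was concluded in 66.8–70.9% with 99,000 per period and 51.8–52.5% with 60,000. Under the shift at 99,000, it was concluded in 0.8–2.8%, and harm was detected in 75–90%.

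**8. ICU transfer.** The figure above 99.9% cannot be checked, because 2% is not defined as relative or absolute and no transfer rate is given. For illustration, with SE = √(4/(49,500 × rate)), assumed day 3–14 transfer rates of 3%, 5%, 10% and 20% give non-inferiority power of 58%, 77%, 96% and 99.9% at HR 1, and 42%, 59%, 84% and 98% at HR 1.02. If the 2% is absolute, the implied HR runs from 1.68 down to 1.11, all outside the 1.1 margin.

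**The case against.** The strongest reply is that the sentence describes detection of a one-day increase, and that 91.5% may be a correct figure for that. Protocol B.2 puts the median hospital stay at about the third day, though for inpatients in general. At a median of 3 days with Efron ties, harm-detection power is 90.8% (lognormal) or 92.8% (log-logistic), both inside the stated interval; Weibull and gamma give about 85–86%. This stands, and a labelling fault is then the likeliest explanation. It does not rescue the claim: power to detect harm is not power to demonstrate safety, which is what the protocol says set the study size.

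Second, 70% depends on inputs the documents do not give: the baseline count, patients taken as admissions, and zero hospital-by-period variance. This also stands, so 70% is conditional. But repeat admissions would have to nearly double the count to reach the 192,000 per period needed, and any hospital-by-period variance lowers the figure.

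Third, the safety paragraphs specify no arm-by-period term, and the protocol mentions an intervention-period comparison just above them. That comparison is described as separate, while both documents make difference-in-differences the main evaluation of all outcomes.

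Fourth, the intervention period ended in December 2023, so precision is fixed and the observed interval will decide non-inferiority. That limits the consequence to how the result is read.

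**Conclusion.** The concern holds. No reading of the documents makes 91.5% the power of the planned LOS non-inferiority test. Under the stated scenario that test concludes non-inferiority in under 5% of trials. At true HR 1 its power is about 70% with 99,000 per period, and 52% to 73% over the other counts examined, before any hospital-by-period variance. Which contrast and rule produced 91.5% cannot be settled from the text. Harm detection with the two-period contrast is the most natural reading; a single-period test at HR 1 also matches, but fits the described two-period bootstrap less well.

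Confidence is high that 91.5% is mislabelled. The 70% is conditional on the stated assumptions. The ICU figure is unverifiable, not shown to be wrong. Because Protocol section D allows enrolment beyond the calculated size, this is a reporting correction that should be made, not a flaw in the trial's conduct.

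**What to change.** - Rerun the existing bootstrap at true HR 1 under the planned difference-in-differences frailty model. Report the probability of concluding LOS non-inferiority, and use that in place of 91.5%.
- Both bootstrap periods come from the same 2019 data and so contain no drift between 2019 and 2023. Show the result with and without a stated hospital-by-period variance.
- Report power to detect the one-day shift separately, with its contrast, implied HR and decision rule.
- State the baseline-period count, and reconcile 99,000 with 60,000.
- For ICU transfer, say whether the 2% is relative or absolute, give the 2019 day 3–14 transfer rate, and report non-inferiority power in the same way.

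The cost is one simulation rerun and revised wording in Protocol C.2.11. The LOS power will probably look less favourable. Patients, margin, test and alpha are unchanged.
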